The key secondary endpoint is the time to resolution of bladder pain as measured by age-appropriate COAs. Resolution of pain is defined as participants achieving a score on the relevant COA that does not exceed "mild pain" (ie, scores of 3 or below on the Bladder Pain/Interstitial Cystitis Symptom Diary [BPIC SD], 0 to 10 NRS capturing participants' worst daily pain among adolescents ≥12 years of age and adults and a parallel assessment for children 3 to 11 years of age as a score that does not exceed 2 on the Wong-Baker FACES® Pain Rating Scale), without use of prescription pain medications or the use of supportive bladder care.

This endpoint will not be assessed in participants <3 years of age.

Other Secondary Efficacy Endpoints

Additional secondary efficacy endpoints include the following:

- Number of days in the hospital (for any reason including, but not limited to, HC) over the 24-week study period.
- Time to resolution of viremia for all target viruses (ie, BKV, AdV, CMV, HHV-6, JCV, and/or EBV) over the 24-week study period (only for participants with detectable viremia at baseline). Evaluation of this endpoint will be based on viremia quantitation performed at the central laboratory. Resolution of viremia will be defined by the lower limits of detection of the assays used.
- Average daily bladder pain (including lower abdominal pain, bladder-related pressure, and/or spasm pain or dysuria) over the initial 6 weeks following randomization.

SAFETY VARIABLES:

The safety endpoints include the following:

- Incidence and severity of acute GVHD (secondary endpoint)
- Incidence and severity of chronic GVHD (exploratory endpoint)
- Incidence and severity of CRS (secondary endpoint)

Safety assessments will also include adverse events, vital signs, 12-lead electrocardiograms (ECGs), physical examination findings, and clinical laboratory assessments.

STATISTICAL ANALYSES:

Summary statistics will be presented by treatment group. Unless otherwise stated, continuous variables will be summarized using the number of non-missing observations, arithmetic mean, standard deviation, median, minimum, and maximum values as descriptive statistics. Categorical variables will be summarized using the frequency count and the percentage of participants in each category as descriptive statistics.

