2.2 Study Design

2.2.1 Overview

This is a Phase 3, multicenter, double-blind, placebo-controlled trial to assess the efficacy and safety of PSL compared to placebo for the treatment of participants with virus-associated HC following allogeneic hematopoietic cell transplant (HCT).

The study hypothesis is that the administration of PSL to participants with virus-associated HC will demonstrate superiority for the time to resolution of HC (as measured by resolution of macroscopic hematuria) compared to participants treated with placebo. The primary hypothesis will be tested in participants with BKV viruria to demonstrate superiority over placebo in this population (BK Intent-to-Treat [ITT] Population). The analysis will also be conducted in all participants with any virus-associated HC (BKV, AdV, CMV, HHV-6, JCV, and/or EBV) in order to evaluate efficacy in this broader population (overall ITT Population).

Participants who meet all of the inclusion criteria and none of the exclusion criteria will be randomized in a sequence in the sequential infusions of PSL cells or placebo and will be monitored for resolution of macroscopic hematuria as defined by the primary endpoint. Randomization will be stratified by

In the dosing strategy being evaluated in this study, all participants will receive infusions of either PSL or placebo separated by (± 3) days.

The specific PSL cell line for infusion will be selected using an electronic-based software system (CytoMatch)

. Cryopreservation media

(without cells) will serve as the placebo and will be identical in volume and appearance to PSL.

AlloVir, Inc.	Statistical Analysis Plan
AVM-003-HC	V1.0 14 November 2023

All randomized participants will undergo regular visual inspections of freshly collected urine samples for: 1) the presence or absence of visible blood, and 2) the presence or absence of blood clots. The schedule of assessments will be determined by the treatment location (inpatient vs. outpatient), time on study (through the end of Week 6 [Day 42] vs. after Week 6), and status of macroscopic hematuria (unresolved vs. resolved), as shown in Table 1. Each time that a participant undergoes a urine visual assessment for Bedi grading, the same sample should be sent for urinalysis.

Treatment	Maaraaania	Time on Study		
Location	Hematuria [1]	Through the End of Week 6 (Day 42)	After Week 6	
Inpatient	Unresolved	Bedi assessment with U/A 3 × per week	Bedi assessment with U/A 2 × per week ≥2 days apart	

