3.2.2 BK Intent-to-Treat Population

The BK ITT Population will include participants in the ITT Population who have BKV detected in the urine. The primary efficacy analysis will be based on the BK ITT Population. In the BK ITT Population definition, BKV identification is determined based on the last available BKV urine viral load test result on or before the randomization date from central laboratory data or if central laboratory data are missing or have "questionable integrity" or "questionable sample integrity," from local laboratory data.

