Time to resolution of viremia for each target virus (ie, BKV, AdV, CMV, HHV-6, JCV, and/or EBV) over the 24-week study period (only for participants with detectable viremia at randomization) will be analyzed using Kaplan-Meier estimates, and treatment effect will be compared using stratified log-rank test and hazard ratio with stratified Cox proportional model. Evaluation of this endpoint will be based on viremia quantitation performed at the central laboratory. Resolution of viremia will be defined by the lower limits of quantitation (LLOQ) of the assays used (BKV, AdV, CMV, HHV-6, JCV are measured in the plasma, EBV is measured in peripheral blood mononuclear cells). Only participants who had viremia at randomization for each target virus will be included in the analysis.

Average daily bladder pain (ie, the participant's average bladder pain over the previous 24 hours) will be recorded daily for the first 6 weeks of the study and once weekly thereafter. The average daily bladder pain will be averaged for each week for the first 6 weeks and starting at Week 7, the single average daily pain score will be recorded. The applicable weekly measures will be summarized by treatment group over the 24-week study period. Only pain assessments

without use of prescription pain medications (not PRN or "as needed") or supportive bladder care will be used.

Time to global impression of hemorrhagic cystitis severity of none or mild, confirmed with 2 consecutive scores, will be analyzed similar to the key secondary endpoint. The analysis will include all the participants who exceed "mild" at randomization. If the scores at randomization are missing, a prior score will be used if available. Otherwise, the participant will not be included in the analysis. Time to resolution will be calculated from the date of randomization to the date of the first time reaching the global impression of hemorrhagic cystitis severity of non or mild, without use of prescription pain medications (not PRN or "as needed") or supportive bladder care. Participants not observed to achieve the threshold will be considered censored at their last follow up.

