Time to resolution of BK viruria will be analyzed using Kaplan-Meier estimates, and treatment effect will be compared using stratified log-rank test and hazard ratio with stratified Cox proportional model. Resolution of viruria is defined by the lower limits of quantitation of the assay used. Resolution of viruria is defined by the lower limits of quantitation of the assay used. Only the participants who had BK viruria at randomization will be included in the analysis. Time to resolution refers to the time from randomization to the initial resolution of viruria.

The numbers and proportions of patients with viremia and viruria with each target virus (ie, BKV, AdV, CMV, HHV-6, JCV, and/or EBV) over time for all the participants as well as for participants who are negative at randomization only.

Length of use of any pain medication(s) (IV, oral, or other), including antispasmodics anticholinergics, and beta-3-agonists, used for control of lower abdominal/bladder pain will be summarized as the total days on any pain medication for each participant.

The use of immunosuppressive agent(s) by specific agent during the study will be summarized by treatment group. The specific dosage information will be listed only.

Number of hospitalizations, number of ICU stays, and number of days of ICU care for any reason will be summarized by treatment group, and reasons will be listed by participant.

Use of antiviral therapies other than cidofovir with potential activity against at least one target virus will be summarized by specific agent during the study. Agents analyzed include foscarnet, ganciclovir, letermovir, maribavir, and valganciclovir. Rd

Overall survival, defined as time to death (from any cause) from the time of randomization in days, will be analyzed as displaying number of participants who died from any cause by week 24 and censored by week 24.

Incidence of relapse or progression of the primary malignancy will also be summarized by treatment group over the 24-week period.

Overall quality of life as measured by appropriate EQ-5D questionnaires will be summarized by treatment for each subdomain over time.

Global impression of change will be summarized by treatment over time.

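### The SAP admits participants with detectable viremia but sets resolution at the quantitation limit, so some may already meet the event at entry

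*SAP*

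**What the plan says.** **Viremia, entry.** SAP 2.1.2, 2.3.2 and 3.4.3 limit this secondary endpoint by detection: "only for participants with detectable viremia at randomization". The paragraph in 3.4.3 closes with "Only participants who had viremia at randomization for each target virus will be included in the analysis", which adds no viral load floor.

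**Viremia, event.** SAP 2.3.2 and 3.4.3: "Resolution of viremia will be defined by the lower limits of quantitation (LLOQ) of the assays used".

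**Protocol.** The Synopsis and Section 7 also admit participants by detectable viremia at baseline, but the event there matches: "Resolution of viremia will be defined by the lower limits of detection of the assays used". Protocol 2.3 and Section 7 likewise use the detection limit for BK viruria.

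**BK viruria (exploratory).** SAP 3.4.3: "Resolution of viruria is defined by the lower limits of quantitation of the assay used". Entry: "Only the participants who had BK viruria at randomization will be included in the analysis". The word detectable is not used here. However, SAP 2.2.1 equates participants with BKV viruria with the BK ITT Population, and SAP 3.2.2 defines that set by detection: "The BK ITT Population will include participants in the ITT Population who have BKV detected in the urine".

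**Testing.** Under SAP 3.4.3 these endpoints are analysed in the BK ITT Population with a stratified log-rank test at one-sided 0.025 and a stratified Cox model. They sit outside the testing hierarchy and have no multiplicity adjustment.

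**The concern.** The SAP moved the event threshold from the detection limit to the LLOQ and left the entry rule where it was. This opens a band between the two limits. A participant whose randomization sample falls in that band is eligible and has, on the SAP's own definition, a value that counts as resolved. Neither document requires a baseline value at or above LLOQ, limits events to post-baseline samples, asks for confirmation, or says how a result that is detected but below LLOQ is coded.

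The SAP handles comparable endpoints differently. Bladder pain (3.4.2) and global impression of severity (3.4.3) admit only participants who exceed mild at randomization or, for pain, are treated as exceeding it. Time to discontinuing supportive bladder care (3.4.3) admits only those receiving it at randomization. The viral endpoints lack that safeguard.

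At stake is the interpretability of the viremia hazard ratio and, more conditionally, the BK viruria one. Participants already below the threshold contribute events that carry little or no information about treatment.

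**Working it through.** **1. Check of the time-to-event set-up.** The documents give no sample size, event count or power for the viral endpoints. The only stated figure to reproduce is the 86.4% power for the primary endpoint (SAP 2.2.3: 105 participants, medians 12 and 6 weeks, 24 weeks of follow-up, 20% censored by 24 weeks, one-sided 0.025).

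- Event rates: ln2/6 = 0.1155 and ln2/12 = 0.0578 per week. Censoring rate: −ln(0.8)/24 = 0.0093.
- P(event by 24 weeks) = λ/(λ+c) × [1 − exp(−24(λ+c))] = 0.879 for PSL and 0.689 for placebo.
- The allocation ratio is redacted. At 1:1, events = 105 × (0.879 + 0.689)/2 = 82.3, and power = Φ(√82.3 × ln2/2 − 1.96) = 88.2%. At 2:1, events are 85.7 and power is 85.6%.

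Both are within 2 points of 86.4%, so the set-up is sound.

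**2. Entry and event side by side.**

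| Endpoint | Entry | Event | Gap |
|---|---|---|---|
| Viremia, protocol | detectable | detection limit | none |
| Viremia, SAP | detectable | LLOQ | detection limit to LLOQ |
| BK viruria, SAP | had BK viruria (detected, via 2.2.1 and 3.2.2) | LLOQ | same, on that reading |

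**3. Power as written and after the fix.** All inputs here are assumptions: 60 viremic participants, true hazard ratio 2, placebo median 8 weeks, 1:1, 10% dropout. Samples fall on the SAP Appendix A Table 3 visits (Weeks 1 to 6, 12, 24). As written, a share f is below LLOQ at entry and has the event at about Week 1 in either arm. After the fix those participants are dropped, leaving 60 × (1 − f).

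| f | Power as written | N after fix | Power after fix | Gain (points) |
|---|---|---|---|---|
| 10% | 57% | 54 | 64% | 7 |
| 20% | 49% | 48 | 56% | 7 |
| 30% | 37% | 42 | 50% | 13 |
| 40% | 30% | 36 | 44% | 14 |

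A separate run of the same case gave 57/46/37/31% and 64/56/51/45%, so simulation differences are up to 3 points.

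**4. Hazard ratio.** A second simulation used 105 participants, medians of 6 and 12 weeks borrowed from the primary endpoint, 20% censoring and 1:1, with the event at entry for the share f. Sampling only at visits already lowers the estimate from 2.00 to 1.79 with nobody below LLOQ.

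| f | HR as written | HR after fix | Power as written | Power after fix |
|---|---|---|---|---|
| 0 | 1.79 | – | 85.2% | – |
| 10% | 1.67 | 1.80 | 75.5% | 83.4% |
| 20% | 1.53 | 1.78 | 62.4% | 77.2% |
| 30% | 1.45 | 1.78 | 52.3% | 72.6% |

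Placing the event at Week 1 instead of entry changes little (HR 1.65 to 1.44 and power 75% to 55% for f of 10% to 30%). With 50 participants and f = 20%, power is 34% as written and 45% after the fix.

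**The case against.** **The band may be empty.** No detection limit, LLOQ or share of participants between them is given. If the two limits coincide, or the laboratory reports below-LLOQ as not detected, nothing is lost. This stands: the wording mismatch is certain, but its size is not.

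**The viruria case is weaker.** The entry sentence says only that the participant had BK viruria, and it stands beside a definition of resolution by LLOQ. It can be read as at or above that limit. Detection enters only through 2.2.1 and 3.2.2. The affected group may also be small, since entry requires Bedi Grade 3 or higher hematuria with viruria and the planned viruria subgroup cut is 10^7 copies/mL. This stands as a reason to state the viruria point conditionally.

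**The event is not certain at Week 1.** If baseline samples do not count, someone below LLOQ at entry may rise above it first. The simulations give every such participant an immediate event, so they are toward the upper end for a given share.

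**The fix does not recover the whole shortfall.** A reader might take the gap from a trial with nobody below LLOQ as the gain available. In step 4 that gap is 85.2 − 75.5 = 9.7, 85.2 − 62.4 = 22.8 and 85.2 − 52.3 = 32.9 points. The fix also drops these participants, so it recovers 83.4 − 75.5 = 7.9, 77.2 − 62.4 = 14.8 and 72.6 − 52.3 = 20.3.

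**Little rests on these tests.** Viremia is tested separately for six viruses within about 105 participants. With 20 viremic for one virus (assumed), power is only about 29% even with no mismatch. This limits the consequence but does not make the definition coherent.

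**Conclusion.** The mismatch between entry and event is in the SAP text for viremia, and it extends to BK viruria if viruria means detected in urine. The expected effect is dilution of the hazard ratio toward 1. Under the assumptions in step 3, resolving it gains about 7 to 14 points of power when 10% to 40% of participants are below LLOQ at entry. The true share is unknown and could be zero.

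A reader might infer a risk of false superiority, or a threat to the trial's main conclusions. The documents support neither. Participants below LLOQ are expected equally in both arms, so the expected effect is conservative, although in a small single-virus subset a chance imbalance could move the estimate either way. Viremia is a secondary endpoint outside the hierarchy and BK viruria is exploratory. The primary endpoint, bladder pain and hospital-day tests do not use these definitions. The point is worth correcting because the estimate is hard to interpret as defined and the change is small.

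**What to change.** In SAP 2.1.2, 2.3.2 and 3.4.3, use one threshold for entry and event:

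- Include participants with a viral load at or above LLOQ at randomization, from the central laboratory or from the local laboratory where SAP 3.1.8 substitutes it.
- Define resolution as the first post-baseline value below LLOQ.
- Apply the same rule to BK viruria, and say there what having viruria at randomization means.
- Summarise participants detected but below LLOQ at randomization separately, by arm, and state how that result is coded.

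Returning the event to the protocol's detection limit would also align the two rules and would exclude nobody, if the sponsor prefers it. Either way, the difference from the protocol's definition should be settled explicitly.

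The cost is a few phrases and an analysis set smaller by the share below LLOQ, which at the upper end of the range shown is 40% and not trivial. No new data are needed.

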Participants not observed to achieve resolution will be considered censored at their last study follow up. Definitive therapies to stop bladder bleeding, such as cystectomy, bladder vessel embolization, cauterization, fulguration, or formalin instillation are permitted. If it is given before or on the day of randomization, the participant will be included in the BK ITT analysis assuming a Bedi of 2 or above. If it is given post randomization, it will be considered treatment failure for the primary endpoint of time to resolution of macroscopic hematuria and will be censored at the last follow-up time of any participant. Participants who discontinued early from the study before

achieving resolution will be censored at the time of last follow up. Participants who died or took non-PSL VSTs prior to reaching resolution will be considered treatment failures and censored at the last follow-up time of any participant.

For Bedi assessments where the grade is not evaluable and the participant is receiving continuous bladder irrigation, has nephrostomy tubes that are uncapped, or the urine is visually bloody, macroscopic hematuria is considered unresolved. For all other Bedi assessments where the grade is not evaluable, the grade is considered missing.

The analysis date for a Bedi assessment is the visual assessment date. If there is no visual assessment date, the urine collection date will be used. Otherwise, the visit date will be used. One Bedi assessment will be selected per analysis date. If there are multiple Bedi assessments on the same analysis date, the worst case is selected. If for a visit, there are Bedi assessments with a visual assessment date or urine collection date, assessments with only a visit date will not be selected.

If there are multiple Hemostick scores on the same date, the highest score will be selected.

If the result of the primary efficacy endpoint (ie, time to resolution of macroscopic hematuria) is statistically significant based on the BK ITT Population, a formal hypothesis test will be conducted sequentially of this same endpoint based on the overall ITT Population using a one-sided 0.025 significance level.

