3.4.2 Key Secondary Efficacy Endpoint

The key secondary endpoint is the time to resolution of bladder pain as measured by age appropriate COAs. Resolution of pain is defined as participants achieving a score on the relevant COA that does not exceed "mild pain" (defined in Protocol Section 7), confirmed with 2 consecutive scores, without use of prescription pain medications (not PRN or "as needed) or supportive bladder care. The relevant COA is the worst daily pain (ie, the participant's worst bladder pain over the previous 24 hours), which is recorded daily for the first 6 weeks of the study and once weekly thereafter. Intermittent missing scores will be omitted.

The analysis will include all the participants whose pain scores exceed "mild pain" at randomization or who use prescription pain medications (not PRN or "as needed") or supportive bladder care at randomization, assuming their bladder pain scores exceed mild. If the scores at randomization are missing, a prior pain score will be used if available. Otherwise, the participant will not be included in the analysis.

Time to resolution will be calculated from the date of randomization to the date of the first resolution of bladder pain. Participants not observed to achieve resolution will be considered censored at their last follow up. The pain scores collected while participants use pain medications (not PRN or "as needed") or supportive bladder care will not be used.

If the result of the analyses of the primary efficacy endpoint is statistically significant based on both the BK ITT and overall ITT Populations, a formal hypothesis test will be conducted sequentially of the time to resolution of bladder pain based on the BK ITT Population in the same manner as described for the primary efficacy analysis of the primary efficacy endpoint, and a one-sided 0.025 significance level will be used. If this result of the analysis of time to resolution of bladder pain based on the BK ITT Population, a formal hypothesis test of this endpoint will then be conducted based on the overall ITT Population using a 0.025 significance level.

A sensitivity analysis of the key secondary efficacy endpoint will also be conducted for the BK ITT population, using a Cox proportional hazards model in order to account for additional potential confounders of the treatment effect. In addition, supportive analyses of the key secondary efficacy endpoint will also be performed based on the BK mITT, BK PP and mITT Populations.

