Secondary efficacy endpoint in the estimand framework is described as follows:

Statistical category	 Estimand: Treatment: Study Treatment (PSL) or Placebo Population: Pediatric and adult participants with virus-associated hemorrhagic cystitis following allogeneic HCT Endpoint (Variable): Time to resolution of bladder pain as measured by age appropriate COAs. Resolution of pain is defined as participants achieving a score on the relevant COA that does not exceed "mild pain" (defined in Protocol Section 7), confirmed with 2 consecutive scores, without use of prescription pain medications (not PRN or "as needed") or supportive bladder care. Intercurrent events: Include intercurrent events from primary efficacy endpoint and 1. Use of prescription pain medications (not PRN or "as needed") or supportive bladder care 2. Early discontinuation from the study treatment before achieving resolution 3. Death due to any cause before achieving resolution 4. Missing daily or weekly assessment of bladder pain 5. Treatment for hemorrhagic cystitis with non-PSL VSTs before achieving resolution 		
	resolution Analysis set Intercurrent event handling Population-le		
	-	strategy	summary (Analysis):
Secondary	BK ITT	 Composite strategy: Data collected while on ICE 1 will not be used for the key secondary endpoint, ie, assuming using ICE 1 is equivalent to pain exceeds "mild pain." Treatment policy strategy: Data collected after occurrence of ICE 2 will be used for the key secondary endpoint. Composite strategy: Participants with ICE 3 will be censored at the last follow-up time of any participant. Hypothetical strategy: ICE 4 will be omitted and next observed assessment will be used Composite strategy: Participants with ICE 5 will be considered treatment failures for the key secondary endpoint of time to resolution of bladder pain and will be censored at the last follow-up time of any participant. 	As primary but using a one-sided 0.025 significance level.
Supportive 1	BK mITT	Same as secondary	Same as secondary
Supportive 2	mITT	Same as secondary	Same as secondary

Subgroup analyses may be conducted for the BK ITT population for age appropriate COAs to evaluate responses in participants who took different outcome measurements, similar to the primary efficacy endpoint.

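### SAP 3.4.3 gives no rule for death before viremia or BK viruria resolution, so ordinary Kaplan-Meier practice would overstate clearance

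*SAP*

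**What the plan says.** In SAP 3.4.3, time to viremia resolution is assessed for each target virus among participants viremic for it at randomization, and "will be analyzed using Kaplan-Meier estimates, and treatment effect will be compared using stratified log-rank test and hazard ratio with stratified Cox proportional model". The exploratory viruria endpoint is specified alike: "Time to resolution of BK viruria will be analyzed using Kaplan-Meier estimates", again with stratified log-rank and Cox. Neither paragraph has a censoring rule or an intercurrent-event rule, and neither mentions death.

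The two leading time-to-event endpoints do address death. For the primary (SAP 3.4.1): "Participants who died or took non-PSL VSTs prior to reaching resolution will be considered treatment failures", and these participants are then censored at the latest follow-up time in the trial, so they stay in the risk set as non-resolvers. The estimand table for the key secondary (SAP 3.4.2), where ICE 3 is death, has: "Participants with ICE 3 will be censored at the last follow-up time of any participant".

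The third endpoint to consider, time to a global impression of HC severity of none or mild, is "confirmed with 2 consecutive scores, will be analyzed similar to the key secondary endpoint".

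**The concern.** A participant who dies with virus still detectable can never clear it. If that participant is censored at death, the Kaplan-Meier method assumes that he or she would have gone on to clear at the same rate as the survivors. One minus Kaplan-Meier then estimates clearance in a population without deaths, which exceeds the proportion who actually clear.

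Deaths are to be expected here. Protocol 1.1 links BKV infection to increased overall mortality, Protocol 3.3 cites high mortality in children with HC after transplant, and overall survival is an endpoint.

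Readers will set viral clearance beside hematuria resolution. The same deaths could count as failures in one and drop out of the other, and that choice is left open for endpoints whose log-rank comparisons are to be reported at the one-sided 0.025 level.

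**Working it through.** **Plan's own figure.** The documents state no figure for these endpoints. The illustration borrows the hematuria planning medians from SAP 2.2.3, so that calculation was checked first. Inputs: 105 in the BK ITT Population, medians 12 and 6 weeks, exponential times, 20% dropout by 24 weeks, one-sided 0.025. The allocation ratio is redacted; 1:1 is assumed.
- Dropout hazard c = −ln(0.8)/24 = 0.00930 per week. Event probability = λ/(λ+c) × (1 − exp(−24(λ+c))).
- Placebo, λ = ln2/12 = 0.05776: 0.689. PSL, λ = ln2/6 = 0.11552: 0.879.
- Events = 52.5 × (0.689 + 0.879) = 82.3.
- Power is 88.2% (Schoenfeld) or 85.6% (Freedman). Simulation with the futility rule gives 87.1%. All are within 2 points of the stated 86.4%.

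**Clearance at 24 weeks.** Assumptions: exponential clearance with hazard λ, and a constant death hazard m = −ln(1−D)/24, where D is the assumed 24-week mortality.
- Deaths censored at death: 1 − KM = 1 − exp(−24λ).
- Deaths counted as never clearing: CIF = λ/(λ+m) × (1 − exp(−24(λ+m))).
- Median of the second curve: −ln(1 − 0.5(λ+m)/λ)/(λ+m).

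Example with a 12-week median and D = 20%: m = 0.00930; CIF = 0.05776/0.06706 × (1 − 0.25 × 0.8) = 0.861 × 0.80 = 0.689, against 1 − KM = 0.750.

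| Mortality D | 1 − KM | CIF | Overstatement (points) | Median with deaths kept (weeks; KM 12) |
|---|---|---|---|---|
| 5% | 75.0% | 73.5% | 1.5 | 12.2 |
| 10% | 75.0% | 72.0% | 3.0 | 12.4 |
| 20% | 75.0% | 68.9% | 6.1 | 13.0 |
| 30% | 75.0% | 65.6% | 9.4 | 13.6 |

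With a 6-week median the overstatement is 1.4, 2.8, 5.8 and 9.0 points.

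**Against sampling error.** At D = 20% with a 12-week median, SE = √(0.689 × 0.311/n). For n = 52 per arm the SE is 6.4 points, and the shift is about 1 SE. Each viremia analysis uses only participants viremic for that virus. At an assumed 20 per arm the SE is 10.4 points, and the shift is about 0.6 SE.

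**Effect on the comparison.** Simulation with 105 participants, 1:1, follow-up to 24 weeks, no other dropout; approximate clearance hazard ratios, above 1 favoring PSL.

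| Clearance medians PSL / placebo (weeks) | Deaths PSL / placebo | HR, death censored | HR, death kept as failure |
|---|---|---|---|
| 6 / 12 | 20% / 20% | 2.05 | 1.93 |
| 6 / 12 | 30% / 10% | 2.08 | 1.67 |
| 6 / 12 | 10% / 30% | 2.05 | 2.25 |
| 12 / 12 | 30% / 10% | 0.99 | 0.87 |
| 12 / 12 | 10% / 30% | 1.00 | 1.15 |

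The death-censored ratio stays near the true clearance ratio (2 or 1) throughout. The ratio with deaths kept as failures moves with the mortality split, in either direction.

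**The case against.** The strongest reply is that the SAP is silent, not wrong. A reader might infer that it directs censoring at death for viremia and viruria, but no sentence says so. The as-observed principle in SAP 3.1.7 concerns missing data and applies equally to the primary, which still counts deaths as failures. This stands: the gap is an unstated rule. It matters because Kaplan-Meier without a death rule is ordinarily run with deaths censored.

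A reader might also infer that death censoring is stated outright for the global impression of severity, from "Participants not observed to achieve the threshold will be considered censored at their last follow up". The documents do not support that. The key secondary carries nearly the same sentence, "Participants not observed to achieve resolution will be considered censored at their last follow up", alongside its explicit death rule, and the severity endpoint is to be analyzed like the key secondary. The natural reading is that the composite rule carries over.

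Nor do the documents or the calculations support a reading that the tests are invalid or tilted toward PSL. With deaths censored, log-rank and Cox address the cause-specific clearance hazard, a legitimate target for a virological endpoint, whereas the composite rule mixes mortality into it. The problem is confined to the clearance curve, its proportions and its median.

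Finally, a mortality difference would not go unseen. Deaths appear in overall survival and the safety tables, and count as failures in the primary and key secondary. Both viral endpoints are outside the hierarchy and unadjusted. All of this limits the consequence, but it does not make the clearance curve right.

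**Conclusion.** The point holds for time to viremia resolution and time to BK viruria resolution. The specified method lacks a death rule, and its ordinary implementation would give clearance proportions and medians that are too favorable. With a 12-week median the excess at 24 weeks is about 1.5, 3, 6 and 9 points at 5%, 10%, 20% and 30% mortality.

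These figures are illustrative. Mortality, the clearance median and the exponential form are all assumptions, and the 12-week value is a planning figure for hematuria. At 5% mortality the shift is small, and in the viremia subsets it is small relative to sampling error. The effect on the between-arm comparison depends on how deaths split and has no fixed direction. The primary conclusion is unaffected, but the rule should be settled before unblinding.

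**What to change.** In SAP 3.4.3, for viremia and BK viruria, do one of the following:
- replace one minus Kaplan-Meier with Aalen-Johansen cumulative incidence, with death before resolution as a competing event; or
- apply the primary's rule, holding participants who die before resolution in the risk set to the latest follow-up time of anyone in the trial.

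Keep the death-censored hazard ratio, labeled as the cause-specific or sensitivity estimate. Given the simulation, cumulative incidence shown beside the cause-specific ratio separates clearance from mortality most clearly.

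For global impression of severity, at most add a sentence confirming that the key secondary's intercurrent-event rules in SAP 3.4.2 apply.

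The cost is a few sentences, minor programming and slightly less favorable clearance figures.
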